2.2.2 Withdrawal of Informed Consent

Any data collected in the clinical database after a subject withdraws informed consent from all further participation in the trial, will not be included in the analysis. The date on which a subject withdraws full consent is recorded in the eCRF.

Additional data for which there is a separate informed consent, e.g., PK, biomarker, etc., collected in the clinical database without having obtained that consent will not be included in the analysis. These data will be excluded by the presence of the appropriate PD criterion.

2.2.3 Subgroup of interest

ORR, DCR and PFS based on local investigator assessment, may be summarized by histological type (squamous vs. non-squamous) in order to examine the homogeneity of treatment effect provided that the primary efficacy analysis based on the FAS is positive.

No formal statistical test of hypotheses will be performed for the subgroup analysis.

ORR and DCR are calculated based on the data from the FAS and the corresponding 95% CI based on the exact binomial distribution ([Clopper and Pearson 1934](#)) will be presented for each subgroup.

PFS will be summarized using the KM method, based on the FAS. Median PFS, with corresponding 95% CI, and 25th and 75th percentiles ([Brookmeyer and Crowley 1982](#), [Klein and Moeschberger 1997](#)) will be presented for each subgroup if data allows it. KM estimates for PFS proportions at specific timepoints (3, 6, 12, and 18 months), along with 95% CI (Greenwood's formula, [Kalbfleisch and Prentice 2002](#)) will also be provided. The number (%) of events and subjects censored will also be summarized by subgroup.

2.3 Subject disposition, demographics and other baseline characteristics

Summaries and listings described in this section will be done by treatment arms based on the FAS.

2.3.1 Subject disposition

The FAS will be used for the subject disposition summary tables and listings. The following will be tabulated:

- Number (%) of subjects randomized/treated;
- Number (%) of subjects who are still on-treatment;
- Number (%) of subjects who discontinued treatment;
- Primary reasons for study treatment discontinuation;
- Number of (%) subjects followed up/not followed after discontinuation of study treatment;
- Number (%) of subjects who discontinued from study;

2.3.2 Basic demographic and background data

Demographic data including age, sex, race, ethnicity, smoking status, baseline weight, baseline height, baseline PD-L1 expression, and ECOG (WHO) performance status will be listed and summarized. Age (18-<65, ≥65 years) categories will be summarized.

2.3.3 Medical History

Medical history and ongoing medical conditions will be summarized by SOC and PT separately and listed, using the latest MedDRA terminology available at the time of reporting.

2.3.4 Diagnosis and extent of cancer

The summary and listing of diagnosis and extent of cancer (disease history) will include details of tumor histology/cytology, histologic grade, predominant histology/cytology, additional histology/cytology, staging system, stage at initial diagnosis, stage at study entry, time (in months) since initial diagnosis of primary site, time (in months) from initial diagnosis to first recurrence/relapse, time (in months) since most recent recurrence/relapse, types of lesions (target and non-target lesions) at baseline, current extent of disease (metastatic sites), and PD-L1 expression. Note that PD-L1 information is taken from the clinical database as standard.

Imputation rules for partially missing dates are provided in [Section 5.1.3.3.1](#).

2.3.5 Protocol deviations

The number (%) of subjects in the FAS with any important PD will be tabulated by the deviation category (selection criteria not met; study treatment deviation; not discontinued after meeting withdrawal criteria; use of prohibited concomitant medication; other deviation). The full list of PDs are documented in the Study Specification Document. Important PDs leading to exclusion from analysis sets will be tabulated separately. ALL PDs will be listed.

2.4 Study treatment, rescue medication, other concomitant therapies, compliance

Summaries and listings described in this section will be done by study treatment arms based on the Safety set. Exceptions are specified in each subsection.

2.4.1 Study treatment

The duration of exposure in weeks of capmatinib + pembrolizumab and pembrolizumab alone, as well as the dose intensity (computed as the ratio of actual cumulative dose received and actual duration of exposure) and the relative dose intensity (computed as the ratio of dose intensity and planned dose intensity) will be summarized by means of descriptive statistics using the Safety set.

Duration of exposure will be categorized into time intervals (e.g., <2 wk, 2-<5 wk, 5-<10wk, 10-<20 weeks, +20 weeks); frequency counts and percentages will be presented for the number (%) of subjects in each interval. Continuous summaries for duration of exposure will be provided using weeks as time units.

The duration of exposure to each treatment will be summarized by means of descriptive statistics using the Safety set.

2.4.1.1 Duration of exposure for investigational drug

Duration of exposure to capmatinib (days) = (last date of exposure to capmatinib) – (date of first administration of capmatinib) + 1.

With:

- The first date of exposure for capmatinib is the first date when a non-zero capmatinib dose was administered and recorded on the study treatment eCRF.
- The last date of exposure to capmatinib is the end date from the last DAR when a non-zero capmatinib dose is recorded in the study treatment eCRF.

Duration of exposure to pembro (days) = (last date of exposure to pembro) – (date of first administration of pembro) + 20.

With:

- The first date of exposure for pembro is the first date when a non-zero pembro dose was administered and recorded on the study treatment eCRF.
- The last date of exposure to pembro is the end date from the last DAR when a non-zero pembro dose is recorded in the study treatment eCRF + 20 days (if no death or no lost to follow-up is observed).

Note: if a subject died or was lost to follow-up before the derived last date of exposure, the last date of exposure to study drug/study treatment is the date of death or the date of last contact, respectively. If the derived last date of exposure goes beyond the data cut-off date, it should be truncated to the date of data cut-off.

Definition of date of last contact can be found in [Section 2.1.1.6](#). Summary of duration of exposure of investigational drug will include categorical summaries (based on clinically meaningful time intervals) and continuous summaries (i.e., mean, standard deviation, etc.) using appropriate units of time.

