2.4.1.2 Duration of exposure to study treatment

Duration of exposure to study treatment (days) = (last date of exposure to study treatment) – (date of first administration of study treatment) + 1.

The date of first/last exposure to study treatment is defined in [Section 2.1.1.2](#).

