2.4.1.3 Cumulative dose

Cumulative dose of a study treatment is defined as the total dose given during the study treatment exposure and will be summarized for each of the study treatment components, respectively.

The **planned cumulative dose** for a study treatment component refers to the total planned dose as per the protocol up to the last date of investigational drug administration. The planned cumulative dose is not summarized/listed. It is used for relative dose intensity calculations.

The **actual cumulative dose** refers to the total actual dose administered, over the duration for which the subject is on the study treatment as documented in the study treatment eCRF.

For subjects who did not take any drug, the actual cumulative dose is by definition equal to zero for that drug.

For capmatinib (continuous dosing), the actual cumulative dose is the sum of the non-zero doses recorded over the dosing period. The planned cumulative dose is the planned starting dose summed over the same dosing period.

For pembro (intermittent dosing), the actual cumulative dose should be defined based on the days when the subject is assumed to have taken a non-zero dose during dosing periods (number of infusions taken over the treatment period). The planned cumulative dose is the planned starting dose summed over the number of expected infusions during treatment period (e.g, a subject treated for 63 days is expected to have three infusions).

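### The pembrolizumab duration formula in SAP 2.4.1.1 adds 20 days a second time, so duration is 19 days too long and dose intensity too low

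*SAP*

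**What the plan says.** SAP 2.4.1.1 gives one duration formula per drug.

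- **Capmatinib:** "Duration of exposure to capmatinib (days) = (last date of exposure to capmatinib) – (date of first administration of capmatinib) + 1".
- **Pembrolizumab:** "Duration of exposure to pembro (days) = (last date of exposure to pembro) – (date of first administration of pembro) + 20".

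The last date of exposure to pembrolizumab is not the infusion date. It is the end date of the last dosing record "when a non-zero pembro dose is recorded in the study treatment eCRF + 20 days", which carries exposure to the end of the 21-day cycle. A note shortens that date to death or last contact "if a subject died or was lost to follow-up before the derived last date of exposure", and truncates it at the data cut-off.

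SAP 2.4.1.2 defines study-treatment duration as last date minus "date of first administration of study treatment) + 1".

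SAP 2.4.1.3 says that "a subject treated for 63 days is expected to have three infusions". The worked examples in SAP 2.4.1.4 use the same 63 days and three infusions to obtain a DI and a planned DI of 200 mg/cycle. That section divides each drug's dose by that drug's own duration of exposure.

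**The concern.** The + 20 in the date definition covers the days after the last infusion. A further + 20 in the formula does that work again, where only the + 1 of an inclusive day count is needed. The formula then contradicts the SAP's own example. A programmer who follows 2.4.1.1 cannot reproduce 2.4.1.4, and one who matches 2.4.1.4 departs from 2.4.1.1.

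The reported pembrolizumab duration and DI are at stake. A fixed 19-day excess distorts short exposures most. Enrollment was halted because the combination was poorly tolerated, with more events leading to interruption or discontinuation of both drugs (Protocol, Amendment 3 rationale). Exposure is therefore important context for the safety results. If pembrolizumab exposure differs between arms, the DI error will differ too. The documents give no exposure data by arm, so the size and direction of that difference are unknown.

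**Working it through.** **Inputs.** 200 mg every 21 days, up to 35 cycles (Protocol 6.1.3 and 6.1.4); last exposure date = last infusion + 20 days (SAP 2.4.1.1); DI = 21 × cumulative dose / duration (SAP 2.4.1.4).

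**The SAP's example.** DI = 21 × 600 / 63 = 200 mg/cycle, so the example is consistent once the duration is 63. The question is whether the formula yields 63. With infusions on Days 1, 22 and 43, the last exposure date is 43 + 20 = Day 63.

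- As written: 63 − 1 + 20 = 82 days; DI = 21 × 600 / 82 = 153.7.
- With + 1: 63 − 1 + 1 = 63 days; DI = 200. This matches.
- Infusion date without the extension, with + 20: 43 − 1 + 20 = 62 days; DI = 203.2. This does not match, and it contradicts the date definition.

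**General form, k on-time infusions, no truncation.** The last infusion is on Day 21(k − 1) + 1 and the last exposure date is Day 21k. As written, duration = 21k − 1 + 20 = 21k + 19; with + 1 it is 21k. The excess is 19 days, or 19/(21k) of the correct duration. DI as written = 21 × 200k / (21k + 19), a shortfall of 19/(21k + 19).

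| Infusions | Days as written | Days with + 1 | Excess | DI as written (mg/cycle) | Shortfall from 200 |
|---|---|---|---|---|---|
| 1 | 40 | 21 | 90.5% | 105.0 | 47.5% |
| 3 | 82 | 63 | 30.2% | 153.7 | 23.2% |
| 6 | 145 | 126 | 15.1% | 173.8 | 13.1% |
| 35 | 754 | 735 | 2.6% | 195.0 | 2.5% |

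**Truncated subjects.** With three infusions and death on Day 50, the last exposure date is Day 50. As written, duration = 50 − 1 + 20 = 69 days; with + 1 it is 50. Nothing is counted twice here, but the formula runs 19 days past death. Truncation at cut-off should rarely arise, because SAP 2.1 places the analysis after all subjects have completed treatment and safety follow-up.

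**Relative dose intensity (RDI).** RDI = (21 × actual dose / D) / (21 × planned dose / D) = actual dose / planned dose. Duration D cancels when planned infusions are counted up to the last administration, as SAP 2.4.1.3 defines. If a programmer instead derived planned infusions from the inflated duration (82 / 21 = 3.9, taken as 4), RDI for perfect dosing would be 600 / 800 = 75%. The SAP does not prescribe that.

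**Study-treatment duration (2.4.1.2).** For pembrolizumab alone, three infusions give 43 − 1 + 1 = 43 days. This does not use the faulty formula.

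**Duration bands.** SAP 2.4.1 says "Duration of exposure will be categorized into time intervals" and lists bands only as examples; 2.4.1.1 asks for categories "based on clinically meaningful time intervals" without cut-points. If the 2.4.1 bands were applied to the component, one infusion would move from 3.0 to 5.7 weeks, three from 9.0 to 11.7 and six from 18.0 to 20.7, each up one band. The other on-time counts up to 35 keep their band: two infusions go from 6.0 to 8.7 weeks, four from 12.0 to 14.7 and five from 15.0 to 17.7, and seven or more already exceed 20 weeks.

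**The case against.** The strongest counter-argument is that this is a slip of one constant whose intent is plain. The date definition and the examples agree on 63 days, so a check against the example would expose it, and the separate programming specification may already be right. The effect is confined to one descriptive duration and one DI summary. The large percentages belong to short exposures. With 50 of 76 randomized subjects still on pembrolizumab on 15-Mar-2021, almost eight weeks after enrollment stopped, single-infusion cases are unlikely to dominate. All of this limits the impact but does not correct the text. SAP section 1 sends changes to the planned analysis through an amendment or addendum, and exempts only minor formatting or spelling mistakes in the output shells.

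Three narrower points:

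- **Who is affected.** The 19 days apply to subjects who received pembrolizumab and have a recorded start date. A combination-arm subject given only capmatinib has no pembrolizumab duration.
- **The condition attached to the + 20 days in the date definition.** It limits the extension to subjects without death or loss to follow-up. Read literally, a subject who died long after the last infusion would get no extension: three infusions would give 62 days as written and 43 with + 1. The note that follows shortens the date only when death or loss comes before the extended date, and that is the sensible governing rule.
- **Another repair.** The bare infusion date with + 21 also gives 43 − 1 + 21 = 63. It would mean rewriting the date definition and the truncation rule, so + 1 is the simpler change.

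**Conclusion.** The formula is wrong as written. It overstates pembrolizumab component duration by 19 days and, for on-time untruncated dosing, understates DI by 47.5% at one infusion, falling to 2.5% at 35. Planned DI takes the same wrong values where the SAP's example gives 200. These figures assume exact 21-day spacing and full 200 mg doses. The documents give no distribution of infusion counts, so the average effect in this trial cannot be stated.

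The consequence is limited to descriptive exposure summaries. PFS and the other efficacy analyses, the 30-day on-treatment window for adverse events and the 2.4.1.2 duration do not use this quantity. It should be corrected before the exposure tables are produced.

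**What to change.** In the pembrolizumab duration formula of SAP 2.4.1.1, replace + 20 with + 1. Keep the last exposure date as last infusion + 20 days, truncated at death, last contact or cut-off as the note states. Three on-time infusions then give 63 days and 200 mg/cycle, and all three duration formulas use the same constant. While the section is open, the condition on death and loss to follow-up could be worded to match the note, so that only events before the extended date shorten it.

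The cost is one constant in the SAP and the matching line in the derivation. No new data are needed.

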2.4.1.2 Duration of exposure to study treatment

Duration of exposure to study treatment (days) = (last date of exposure to study treatment) – (date of first administration of study treatment) + 1.

The date of first/last exposure to study treatment is defined in [Section 2.1.1.2](#).

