2.1.1.2 Date of first/last administration of study treatment

For PEMBRO single agent treatment, the date of first (last) administration of study treatment is derived as the first (last) date when a non-zero dose of PEMBRO was administered and recorded on the DAR eCRF.

For INC280 + PEMBRO, the date of first (last) administration of study treatment is derived as the first (last) date when a non-zero dose of any component of study treatment was administered and recorded on the DAR eCRF.

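### SAP 2.4.1.2 ends exposure to study treatment on the day of the last dose, so subjects who end on a pembrolizumab infusion lose up to 20 days that SAP 2.4.1.1 counts

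*SAP*

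**What the plan says.** SAP 2.4.1.2 computes the duration of exposure to study treatment as the last exposure date minus the first administration date, plus one day. It supplies no end date of its own: "The date of first/last exposure to study treatment is defined in" Section 2.1.1.2.

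Section 2.1.1.2 deals with administration rather than exposure. For pembrolizumab alone it takes "the first (last) date when a non-zero dose of PEMBRO was administered and recorded on the DAR eCRF". For the combination it takes "the first (last) date when a non-zero dose of any component of study treatment was administered". Neither rule adds any days after the last dose.

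Elsewhere the SAP treats one infusion as covering a 21-day cycle. Section 2.4.1.1 sets the last date of pembrolizumab exposure 20 days after the last non-zero dose, cut short at death, last contact or data cut-off. Section 2.4.1.3 says that "a subject treated for 63 days is expected to have three infusions", and the dose intensity example in 2.4.1.4 uses the same 63 days.

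The result is reported by arm in weeks and also in bands: "Duration of exposure will be categorized into time intervals" (SAP 2.4.1), with example limits at 2, 5, 10 and 20 weeks.

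**The concern.** In the control arm, study treatment is pembrolizumab and nothing else. Sections 2.4.1.1 and 2.4.1.2 should therefore give the same end of exposure for a control subject, and they do not.

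The rule also behaves differently according to which drug came last. Capmatinib is taken daily from Day 1 to Day 21 of each cycle (Protocol 6.7.2). A combination subject who takes tablets to the end of the final cycle is credited with all 21 days of it. A subject whose last dose is an infusion is credited with one day of that cycle.

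Enrollment was halted because the combination was poorly tolerated (Protocol, Amendment 3 rationale), so readers will look at exposure by arm next to the safety tables. The error is largest in relative terms for subjects who stopped early: a control subject with one infusion would be reported as exposed for one day.

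**Working it through.** **Inputs**
- Cycle length: 21 days in both arms (Protocol 6.1.3). With no delays, infusions fall on Days 1, 22, 43 and so on, and infusion n falls on day 21(n − 1) + 1.
- Capmatinib: daily, Day 1 to Day 21 of each cycle (Protocol 6.7.2).
- End-date rules: SAP 2.1.1.2, 2.4.1.1 and 2.4.1.2.
- Subjects: 51 combination and 25 control randomized; 50 ongoing on single-agent pembrolizumab on 15-Mar-2021 (Protocol, Amendment 3 study update).

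**The SAP's own figure: three infusions = 63 days.** The last infusion is on Day 43.
- Last infusion plus 20 days, counted inclusively with a single +1: (43 + 20) − 1 + 1 = 63. This reproduces the example.
- SAP 2.4.1.2 with 2.1.1.2: 43 − 1 + 1 = 43. It is 20 days short.
- SAP 2.4.1.1 as written, which adds 20 to the end date and 20 again in the formula: (43 + 20) − 1 + 20 = 82. This is a separate slip. Correcting it restores 63 in 2.4.1.1 and leaves 43 in 2.4.1.2.

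**General form under 2.4.1.2, for n cycles each opened by an infusion**
- Last dose is an infusion (either arm): 21(n − 1) + 1 days.
- Last dose is a tablet on day k of the final cycle: 21(n − 1) + k days.
- Difference: k − 1 days. For k = 1, 7, 14 and 21 this is 0, 6, 13 and 20 days.
- Shortfall against the full 21n days: 20 days after a final infusion, and 21 − k days after a final tablet on day k. Truncation at death, last contact or cut-off makes it smaller.

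**Bands at the maximum gap (k = 21)**

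| Cycles | Ends on infusion | Tablets to cycle end | Band changes? |
|---|---|---|---|
| 1 | 1 day (<2 wk) | 21 days (2–<5 wk) | yes |
| 2 | 22 (2–<5) | 42 (5–<10) | yes |
| 3 | 43 (5–<10) | 63 (5–<10) | no |
| 4 | 64 (5–<10) | 84 (10–<20) | yes |
| 5 | 85 (10–<20) | 105 (10–<20) | no |
| 6 | 106 (10–<20) | 126 (10–<20) | no |
| 7 | 127 (10–<20) | 147 (20+) | yes |
| 8 | 148 (20+) | 168 (20+) | no |

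Beyond eight cycles both columns stay in the top band.

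**How many combination subjects end on an infusion.** If all 25 control subjects were among the 50 ongoing on 15-Mar-2021, then 50 − 25 = 25 combination subjects were ongoing on pembrolizumab alone. With fewer ongoing controls the number is higher. So at least 25 of 51 (49%) were on infusions only. Assuming each had an infusion after the last tablet, their gap to control is zero. At most 51 − 25 = 26 combination subjects remain, and the documents do not say how many of those took a tablet after their last infusion or on which day.

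**The case against.** The strongest reply concerns reach. A reader might infer that combination exposure always ends at the last daily tablet, so that the control arm as a whole is reported with 20 days less exposure for the same number of cycles. The documents do not support that. The combination rule takes the last dose of either drug, and the sponsor stopped capmatinib in every ongoing combination subject, so about half of that arm or more would end on an infusion like the controls. Twenty days is the maximum gap, reached only with tablets through day 21 of the final cycle. If capmatinib stopped on or before the last infusion day, there is no gap. Protocol 6.7.2 allows pembrolizumab to continue after capmatinib is stopped for toxicity, so a completed final cycle of both drugs cannot be assumed.

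A reader might also infer that the adverse event comparison is biased. No planned adverse event table uses this duration: SAP 2.8.1 reports numbers and percentages of subjects. Dose intensity and relative dose intensity use component durations (2.4.1.4), and the on-treatment window is tied to last administration (2.1.1.5). Exposure is also summarized for each drug separately, so pembrolizumab exposure can be compared between arms without 2.4.1.2, once the formula in 2.4.1.1 is corrected.

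Finally, this may be a cross-reference slip. The note in 2.4.1.1 on death or loss to follow-up before a derived last exposure date names study treatment as well as study drug. Nobody can die before a dose actually received, so the note suggests that a carried-forward date was intended here too.

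The points on reach and consequence stand, and they limit the finding. The last point supports the correction: the extension is not written for study treatment, and the reference in 2.4.1.2 leads to a section without it.

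**Conclusion.** SAP 2.4.1.2 is wrong as written. It disagrees with 2.4.1.1 on when exposure to the same drug ends, and it gives 43 days where the SAP's examples give 63.

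- **Shortfall.** Up to 20 days for every subject whose last dose is an infusion: all control subjects and the combination subjects who ended on pembrolizumab.
- **Inconsistency.** Combination subjects whose last dose is a tablet on day k of the final cycle gain k − 1 days, at most 20, over a control subject with the same number of infusions. They gain the same over combination subjects who ended on an infusion, so the rule is uneven within that arm as well. The size of this subset is not given.
- **Consequence.** One descriptive summary and its bands. At the maximum gap the example bands shift at 1, 2, 4 and 7 cycles; the SAP offers those limits only as examples. No efficacy estimate or safety count changes.

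The arithmetic assumes infusions exactly every 21 days and a final cycle that opened with an infusion. If capmatinib continued for further cycles after pembrolizumab stopped, the extra days are genuine exposure and not part of this discrepancy.

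**What to change.** In SAP 2.4.1.2, replace the reference to 2.1.1.2 for the end date. For both arms, define the last date of exposure to study treatment as the later of (a) the last capmatinib dose date and (b) the last pembrolizumab infusion date plus 20 days, truncated at death, last contact or data cut-off as in 2.4.1.1. Keep a single +1 in the duration formula. Three infusions then give 63 days in either arm, and n completed cycles give 21n.

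Applying the extension to the control arm alone would not do: combination subjects who ended on an infusion would then be 20 days short of control.

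Keep 2.1.1.2 for the 30-day on-treatment safety window, where the date of last administration is what is needed. In the same edit, change the second +20 in the pembrolizumab formula of 2.4.1.1 to +1.

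The cost is one sentence in 2.4.1.2, one constant in 2.4.1.1 and the matching derivations in the dataset specifications. No new data are needed.
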